**Data Analysis**

All the analyses will be descriptive. Continuous variables will be described by their mean, standard deviation, and median, first quantile (Q1), third quantile (Q3), minimum and maximum. Categorical variables will be described as total number and relative percentage per category.

**Main analysis**

A description of the following outcomes of interest related to process indicators will be performed:

- Measures of the extent of implementation of the original plan, and/or variations in its delivery, at each participating country level.
- Knowledge and Behaviour

The primary analysis population will include the total number of HCPs who returned a valid questionnaire. The proportions of correct and appropriate answers to selected questions will be expressed among HCPs who provided answers to those questions (the missing data will not be counted as a denominator in proportions). Also, the proportion of HCPs who provided correct answers to 70%, 80%, 90% and 100% of the questions will be derived. Last, the proportion of HCPs who have provided correct answers to each of the questions will also be generated.

The threshold of the satisfactory rate is defined as 80% of the HCPs providing correct responses for the following questions:

- 1 The first knowledge question (key question) for both prescribers and non-prescribers.  
AND
- 2 At least five out of seven behaviour questions for prescribers.  
AND
- 3 At least two out of three behaviour questions for non-prescribers.

The statistical results for knowledge and behaviour will be presented overall and then at country level broken down by subpopulation of interest, i.e. type of HCP.

**Exploratory analysis**

Of note, similar aRMMs were distributed to HCPs in Europe after the market authorisation was granted to the first-in-class compound (daratumumab). A research article published in February 2021 reported that a total of 408 participants completed the questionnaires. The risk and content of educational materials developed for daratumumab are similar and one can assume that the target population of HCPs is also similar to that of isatuximab. Therefore, a discussion about the proportions observed after the implementation of the risk minimisation measures could be considered against those reported from the daratumumab survey (i.e. pre-post designs), provided that they are available (i.e. publicly disclosed) at the time of this study report preparation/ submission. However, due to the lack of access to patient-level data, no statistical comparison will be performed.

**Milestones**

Milestone	Planned date
Protocol submitted to PRAC	December 2020 (based on EC decision in June 2020)
Protocol approval by PRAC	Estimated Q1 2022
Start of data collection	within 3 months after PRAC approval of protocol (estimated Q1-Q2 2022)
End of data collection	Estimated Q1 2023
Registration in the EU PAS register	Before data collection starts
Final report of study results	Within 6 months after end of data collection (estimated Q3 2023)

## 5 Amendments and Updates

Amendment or Update No.	Date	Section of Protocol	Amendment or Update	Reason
None	Not applicable	Not applicable	Not applicable	Not applicable

## 6 Milestones

Milestone	Planned date
Protocol submitted to PRAC	December 2020 (based on EC decision in June 2020)
Protocol approval by PRAC	Estimated Q1 2022
Start of data collection	within 3 months after PRAC approval or protocol ( estimated Q1-Q2 2022 )
End of data collection	Estimated Q1 2023
Registration in the EU PAS register	Before data collection starts
Final report of study results	Within 6 months after end of data collection ( estimated Q3 2023 )

## 7 Rationale and Background

Multiple myeloma (MM) is a malignant plasma cell disease that is characterised by clonal proliferation of plasma cells in the bone marrow and the production of excessive amounts of a monoclonal immunoglobulin. The estimated 5-year prevalence of multiple myeloma in Europe reported by the International Association for Research on Cancer (in 2018) is 120 391 (16.2 per 100,000).(1) MM is a disease predominantly associated with advanced age with more than 80% of patients aged 60 years or older. Patients with MM are likely to develop bone pain, bone fractures, fatigue, anaemia, infections, hypercalcemia, and renal function impairment, because of their disease.(2)

The disease course for MM varies with the aggressiveness of the disease and related prognostic factors. Treatment options and survival are based on the patient's age, fitness, and disease status. Patients under the age of 65, and presenting with symptomatic active disease in good physical health, will generally receive initial therapy with autologous stem cell transplantation (ASCT).(3) To achieve cytoreduction of the disease before collecting stem cells, induction chemotherapy is administered. In the long term, however, there is currently no cure for multiple myeloma, which is characterised with frequent relapses.

Isatuximab is a naked monoclonal antibody targeting a cluster of differentiation (CD) 38, a cell surface antigen expressed in haematological malignancies from B-lymphocyte, T-lymphocyte and myeloid origin. Isatuximab has been investigated with various regimens, including in combination with pomalidomide and dexamethasone for the treatment of multiple myeloma in a Phase 3 randomised, open-label, multicentre study in patients with refractory or relapsed and refractory multiple myeloma (ICARIA-MM).(4)

The approved therapeutic indication for SARCLISA (isatuximab) is in combination with pomalidomide and dexamethasone, for the treatment of adult patients with relapsed and refractory multiple myeloma who have received at least two prior therapies including lenalidomide and a proteasome inhibitor and have demonstrated disease progression on the last therapy. On 25 February 2021, the CHMP Positive Opinion was received, and on 15 April 2021, the European Commission decision was issued for the extension of indication for SARCLISA (isatuximab) in combination with carfilzomib and dexamethasone (kd) for the treatment of adult patients with relapsed multiple myeloma who have received at least one prior therapy.(9)

The European Commission decision for marketing authorisation approval was obtained on 30 May 2020.

Routine pharmacovigilance will be carried out to monitor the safety of SARCLISA. Additional risk minimisation activities are proposed to minimise the following important identified risk: interference for blood typing (minor antigen) (positive indirect Coombs' test). The rationale for these additional risk minimisation activities is that isatuximab binds to endogenous CD38 found at low levels on red blood cells (RBC) and may interfere with blood bank compatibility testing, including antibody screening and cross-matching. Lack of RBC phenotyping prior to starting the isatuximab treatment, could therefore result in adverse clinical outcomes for the patient due to delaying a transfusion or, in the case of urgent transfusion, there is a small risk of transfusion related haemolysis. In clinical trials, specific instructions are provided to investigational sites to have blood typed and screened performed prior to the initiation of therapy; in the pivotal clinical trial (Study EFC14335), the proportion of patients who needed red blood cells transfusion was 30% and no RBC transfusion-related complications associated with interference for blood typing were reported.

The goal of the educational materials developed as additional risk minimisation measures (aRMMs) is to:

1. Inform healthcare professionals (HCPs) that isatuximab is associated with risk of interference with blood typing
2. Guide HCPs on the specific actions to manage the interference and avoid possible resulting adverse clinical consequences.

Safety messages listed in the educational materials target two types of HCPs:

- 1 Medical specialists, such as haematologists and oncologists who prescribe isatuximab to patients (prescribers)
- 2 HCPs who work in the blood banks and transfusion centres and provide blood product to patients treated with isatuximab (non-prescribers).

More specifically, messages that are targeting prescribers include the length of interference and the actions to take before, during and after isatuximab treatment (e.g., blood typing, blood compatibility profile in the Patient Card, manage blood transfusions); messages targeting non-prescribers include the mechanism of interference, specific types of blood compatibility test affected, and interference mitigation methods for blood transfusion.

Some countries (Australia) have established a policy for phenotype screening prior to the initiation of therapy with CD38 class agents, following the marketing approval of the first in class anti-CD38 (daratumumab) and/or methods to mitigate the risks of interference,(5) and such methods are included in the educational materials developed for isatuximab. The extent of the compliance to this risk mitigation in clinical practice, however, is not known.

It is critical to ensure that key safety precautions conveyed in the educational materials are well understood and adhered to by the HCPs (both prescribers and non-prescribers) in the real-world setting. Educational materials include a brochure ([Appendix A](#)) that will be distributed to both types of HCPs, as well as a Patient card ([Appendix B](#)) that will be provided to patients via their HCPs.

According to the GVP Module XVI – Risk minimisation measures: selection of tools and effectiveness indicators (Rev 2) dated 28 March 2017,(7) evaluating the effectiveness of aRMMs is necessary to establish whether an intervention has been effective, and, if not, why and which corrective actions are necessary.

This study is therefore designed to evaluate the following aspects of the aRMM: the process itself (i.e. to which extent the materials have been implemented as planned) and its impact on knowledge and behavioural changes in the target audience.

## 8 Research Questions and Objectives

The study aims to assess the effectiveness of the isatuximab Educational Materials in terms of process indicator, meaning implementation, knowledge and behaviour with respect to the safety messages conveyed in these materials.

### Objective

- 1) Describe the implementation of the aRMMs to the target population, the time period(s) of implementation in each participating country (starting from local regulatory approval) and materials used.
- 2) Assess the knowledge of the target audience about the risk and its management
  - Messages specific to the prescribers (HCPs in oncology/haematology)
  - Messages specific to the non-prescribers (HCPs in blood banks/transfusion centres)
- 3) Assess the behaviour of HCPs with respect to the safety messages

- Messages specific to the prescribers (HCPs in oncology/haematology)
- Messages specific to the non-prescribers (HCPs in blood banks/transfusion centres)

## **Hypothesis**

We hypothesize that:

- At least 80% of the HCPs (both prescribers and non-prescribers) will provide correct responses to the first knowledge question, which is identified as the key question.

**AND**

- 80% of the prescribers will provide correct responses to at least five out of seven behaviour questions.

**AND**

- 80% of the non-prescribers will provide correct responses to at least two out of three behaviour questions.

## **9 Research Methods**

### **9.1 Study Design**

This is a non-interventional cross-sectional study among HCPs involved in the treatment of MM with SARCLISA (isatuximab) in selected European countries.

The study is a cross-sectional survey planned to be conducted within 12-18 months after implementation of educational materials in each country. The surveys will be conducted online, using structured questionnaires, comprising close-ended questions where the response format is either the selection of a single response or selection of a number of responses as appropriate. Information will be collected from HCPs using the online LiveTracker™ platform. LiveTracker™ is a cloud-based, real-time, continuous electronic data collection platform tracker that delivers real-world evidence data.

This PASS will be conducted according to the Guideline on good pharmacovigilance practices (GVP) – Module VIII (Rev 3) dated 9 October 2017 (7) and according to the GVP Module XVI (Rev 2) dated 28 March 2017 (EMA/204715/2012 Rev 2).

## 9.2 Setting

The study will be conducted in selected European countries after the launch of isatuximab (SARCLISA) and the distribution of the educational materials to the HCPs (see Table 1). Up to 9 countries may be included in this study, where country inclusion will be based on:

- Isatuximab launch dates
- Date of distribution of the educational materials
- Target population size (oncology centres and blood banks)
- Feasibility in terms of regulatory implementation at national level
- Representativeness of Europe
  - Country population size
  - Country geographic location

Table 1 - List of launch date and distribution status of educational materials in each country

Country	Actual/Estimated Launch Date	Implementation of EMs	Recipients	Comments
Switzerland	30 APR 2020	JUN 2020 (digital) AUG 2020 (hardcopies) JUN 2021 (website)	About 50 maximum physicians in Onco/Haematology, blood banks (BB) and blood donation centres	Hospitals have either their own BB or work with a centralized one. In some cases, there is no BB and this is covered by the Blood donation center
Austria	JUL 2020	JUN- 2020 (hardcopies) Distribution of the revised version completed in July 2021	29 Internal Medicine, 16 Oncology, 9 Haemato-Oncology, 1 Haematology, 2 immunology serology transfusion medicine, 9 Blood bank transfusion medicine, regional blood donation centre, and 58 hospital pharmacies (for information)	Oncologists and Haematologists are specialised sub-units of Internal Medicine

Country	Actual/Estimated Launch Date	Implementation of EMs	Recipients	Comments
France	SEP 2020 (post ATU*)	AUG 2020 Distribution of the revised version planned to be completed by 31Dec2021	778 Oncologists + 2,002 Haematologists + national centre of BB from where EMs will be forwarded to the 13 regional centres.	Based on ATU* experience (Aug 2019, 399 patients), Haematologists made most of prescriptions.
Sweden	01-JUL- 2020 (not reimbursed)	JUN 2020 (mail+ website)  Distribution of the revised version completed in June 2021	Haematologists (293) Head of Haematologist Department, BB and transfusion centres (104)	All prescriptions by Haematologists
Finland	15 SEP 2020 (not reimbursed)	SEP / OCT and NOV 2020 + ad hoc distribution in Q1/Q2 2021 (email and mail)  Distribution of the revised version completed in Sep 2021	Haematologist (76), BB (10)	All prescriptions by Haematologists
The Netherlands	OCT 2020 (reimbursed)	SEP 2020 (mail + website)	1,335 Oncologists / Haematologists + 631 hospital pharmacists + 350 clinical chemists (all HCPs in-training included) and 21 blood banks relevant societies for professionals	
UK	01 JUN 2020	APR-AUG 2020 (mail)	N=5061	
Poland		AUG-SEP 2020 (email, mail and website) Distribution of the revised version completed in Sep 2021	Physicians: haematologists (326), oncologists (705), specialists in transfusiology (97). National and regional consultants in haematology, oncology and transfusiology (48).	

Country	Actual/Estimated Launch Date	Implementation of EMs	Recipients	Comments
			Multiple myeloma treatment centres (53). Regional and field blood-donation centres (163).	
Germany	01 MAR 2021	JAN -MAR 2021 (mail and website)  Distribution of the revised version completed in June 2021	Oncologists and haematologists: 3655  Blood banks: 170	
Italy	29 MAR 2021	APR 2021 (email)	Haematologist, oncologists and scientific societies: 10 107	
Hungary	Planned NOV 2021	No distribution (product not yet launched)	To be provided later	

\* ATU: temporary authorisation for use ‘autorisation temporaire d’utilisation”

Abbreviations: BB = Blood Banks; EM = Educational Materials; HCP = healthcare professional; UK = United Kingdom

Since country inclusion is based on the date of launch and distribution of the educational materials, target population size, and representativeness of Europe, we will include, at minimum, the following five countries: France, Switzerland, Austria, Sweden, and the Netherlands. There will be a maximum of nine countries included in this study and the other potential countries include (but are not restricted to): Germany, Finland, United Kingdom (UK), Italy, Poland and Hungary. Also, the necessary Ethics/Regulatory requirements to conduct this study may generate some changes in this list.

Current countries listed are the ones with educational materials expected to be implemented by the end of 2021 (Table 1) as data collection will occur in each country 12-18 months post-implementation. The following EU countries cannot participate because SARCLISA (isatuximab) will not be marketed or educational materials will not be implemented by the end of 2021 in order to complete data collection by Q1 2023: Bulgaria, Cyprus, Estonia, Greece, Ireland, Latvia, Lithuania, Spain and Romania.

### 9.2.1 Study Sites

Not applicable

---

## 9.2.2 Study Population Selection Criteria

HCP selection is based on the inclusion and exclusion criteria listed below.

HCPs who meet each of the inclusion criteria and none of the exclusion criteria are eligible to participate in this study.

### Inclusion Criteria

- The HCP is involved in the management and follow-up of multiple myeloma, such as oncology/haematology specialists and HCPs associated with blood banks/transfusion centres who have not necessarily prescribed isatuximab.
  - Prescribers (Oncologists/Haematologists): The HCP has prescribed isatuximab at least once.
  - Non-prescribers (Blood banks/transfusion centres): The HCP has provided blood products at least once for a patient treated with isatuximab.
- The HCP provides consent to participate.

### Exclusion Criteria

- The HCP has previously been enrolled in this study.

## 9.2.3 HCP Recruitment

Recruitment of HCPs will occur mainly from a multi-national panel (the LiveTracker™ panel). LiveTracker™ is a cloud-based, real-time, continuous electronic data collection platform that allows collection of real-world evidence data from HCPs across multiple continents. Multi-national panels of physicians in LiveTracker™ exist across haematology-oncology therapeutic areas, including a panel for MM. In order to optimise recruitment, educational material distribution lists will be used when possible as a complement.

To be part of the LiveTracker™ physician panel, physicians are screened, including a credentials check, and fill out an initial profiling survey that includes answering questions about practice setting, caseload, specialities, etc. For participation in this study, HCPs will be screened based on the following criteria to identify qualified participants:

- 1) Prescribers: haematologist/onco-haematologist who prescribed isatuximab at least once.

The prescribers are medical specialists who are responsible for initiating the treatment, communicate with the patient and make the appropriate decision(s) if a transfusion is needed. Depending on the country, they initiate the blood compatibility profile,

manage the transfusion, including the order of blood products or refer the patient to a transfusion department / blood bank.

- 2) Non-prescribers: HCPs work in the blood banks/transfusion centres who have provided blood products at least once for a patient treated with isatuximab.

Depending on the country, HCPs affiliated with transfusion departments or blood bank may oversee the blood compatibility profile, identify and deliver the blood products. However, in most countries, they do not communicate with the patient.

The potential pool of HCP participants is shown in Table 2, which is mainly based on the current number of HCPs in the haematologist and haemato-oncologist panels in LiveTracker™. LiveTracker™ is actively building up a panel of HCPs working in the blood banks/transfusion centres to have sufficient number of HCPs to send invitation emails to, as presented in Table 3 Column C.

**Table 2. LiveTracker™ haematologist and haemato-oncologist panels in each country.**

	Total Number of HCPs
Austria	538
Switzerland	1,135
Germany	4,696
Finland	156
France	3,549
UK	4,061
Hungary	120
Italy	3,298
Netherlands	647
Sweden	594
Poland	288
Total	19,082

Abbreviations: HCP = healthcare professional; UK = United Kingdom

HCP prescribers (haematologist/onco-haematologist) and non-prescribers (HCPs working in the blood banks/transfusion centres) will be recruited the same way through the LiveTracker™ panel. From the overall country-specific list of HCPs, invitation e-mails will be sent to HCPs to explain the objective of the study and their expected involvement, as well as provide a link to the electronic survey.

To maximise the response rate if the objective of 400 HCPs is not reached, multiple reminders will be sent. If recruitment rate is low after three reminders, we may consider different strategies including broadening the inclusion criteria to also include any HCPs who have prescribed other anti-CD38 therapy (prescribers) or who have provided blood products for a

patient treated with other anti-CD-38 therapy (non-prescribers). This change would be implemented after a protocol amendment is approved.

To minimise selection bias, the number of HCPs is targeted based on the combination of the country population, target population (haematology and haemato-oncology centres and blood banks), and date of distribution of educational materials. Since this survey is targeting HCPs instead of patients, this recruitment approach will reflect the proportion of HCP prescribers/non-prescribers within these countries. Approximately 400 HCPs will be included in this study. It is expected that the European Union countries with a large population will have a greater number of HCPs included in the study compared to countries with a smaller population. In addition, the number of HCPs included per country will vary based on the volume of distribution of educational materials for each country. Recruitment strategy for HCPs will vary among countries as the aim will be to recruit HCPs who properly represent the HCP specialities and practice settings where educational materials are distributed in each country. Additional factors that will be considered during recruitment, in efforts for representativeness, include recruiting HCPs from different regions in each country, and recruiting HCPs with varying numbers of patients treated with isatuximab.

The final response rate is estimated to be 4.4%-6.8% based on historical LiveTracker™ data (17% of HCPs will respond to communication emails, and of those who respond, approximately 26% to 40% will be eligible and will complete the survey). In order to obtain close to 400 completed questionnaires, a total of approximately 6,000 to 9,000 invitation emails will be sent (it varies among country and will be adjusted based on the response rates of each country and each types of HCPs).

These invitation emails are planned to be sent using a stratified random sampling method, however, further random sampling steps after the initial email is likely not feasible since the goal is to maximize responses. A few reasons it is not feasible include 1) the low numbers of HCPs in some countries; 2) the low expected response rate (4.4%-6.8%).

HCP non-prescribers are targeted to be, at minimum, 10% to 25% of the total HCPs, meaning that the prescribers are targeted to be, at maximum, 75% to 90% of the total HCPs. Considering that the proportion of each types of HCPs may vary among countries based on the country-specific distribution of educational materials, it is acceptable that, in certain countries, the final proportion of non-prescribers may exceed 25%.

Table 3 presents the number of invitation emails to be sent and the estimated target numbers of prescribers and non-prescribers in each potential study country.

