**Table 3. Estimated target number of HCPs per country**

Country	A Estimated Total Number of Invitation Emails*	B Estimated Number of Invitation Emails to HCP Prescribers	C Estimated Number of Invitation Emails to HCP Non- prescribers (10-	D Target Total Number of HCPs (4.4- 6.8% of column A)	E Target Number of HCP Prescribers (75-90% of column D)	F Target number of HCP Non- prescribers (10- 25% of column D)

		(75-90% of column A)	25% of column A)			
Austria	250-400	190-360	25-100	10-15	8-14	1-4
Switzerland	250-400	190-360	25-100	10-15	8-14	1-4
Germany	1250-1750	940-1580	125-440	50-70	38-63	5-18
Finland	100-150	75-135	10-40	5-10	4-9	1-3
France	1250-1750	940-1580	125-440	50-70	38-63	5-18
UK	1250-1750	940-1580	125-440	50-70	38-63	5-18
Hungary	250-400	190-360	25-100	10-15	8-14	1-4
Italy	1250-1750	940-1580	125-440	50-70	38-63	5-18
Netherlands	250-400	190-360	25-100	10-15	8-14	1-4
Sweden	100-150	75-135	10-40	5-10	4-9	1-3
Poland	100-150	75-135	10-40	5-10	4-9	1-3
Total	6000 - 9000	4500-8100	600-2250	up to 400	300-360	40-100

\* Estimated based on historical LiveTracker™ data.

Abbreviations: HCP = healthcare professionals; UK = United Kingdom

[figure not shown]
HCPs will provide consent and data will be anonymous for the Market Authorisation Holder (MAH).

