behaviour in countries where isatuximab was launched in 2020 or planned to be launched by early 2021, therefore not fully representative of all European countries where isatuximab will eventually be used. In addition, the volume of isatuximab use in the selected countries could also vary and may fluctuate, therefore, the proportion of HCPs in selected countries is based on the potential pool of HCPs rather than the volume of isatuximab use in each country. The educational material distribution strategy the definition and size of the target audience is expected to vary across countries. Consequently, the proportion of HCPs having received the educational material among the invited and participating HCPs might also vary across countries. The implementation results will need to be interpreted in the light of each country-specific distribution strategy.

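### Table 3 allots Hungary 190-360 prescriber invitations from a panel of 120 with no materials yet distributed, and ranks Hungary above Poland and Austria above Sweden against both panel size and distribution volume

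*Protocol*

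**What the plan says.** Section 9.2.3 offers the country allocation as a guard against selection bias. It states that "the number of HCPs is targeted based on the combination of the country population, target population" and the date of distribution, and adds that "the number of HCPs included per country will vary based on the volume of distribution of educational materials for each country". Section 9.9 says that "the proportion of HCPs in selected countries is based on the potential pool of HCPs rather than the volume of isatuximab use". Recruitment is mainly from the online panel, with distribution lists as a complement where possible.

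The numbers are in three tables:

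- Table 1 (section 9.2) lists recipients of the materials. For Hungary it reads "No distribution (product not yet launched", with launch planned for November 2021 and recipient numbers to follow. For Poland it begins "Physicians: haematologists (326), oncologists (705), specialists in transfusiology (97" and adds consultants and centres.
- Table 2 gives the "haematologist and haemato-oncologist panels in each country", which is the prescriber pool.
- Table 3, "Estimated target number of HCPs per country", gives total, prescriber and non-prescriber invitations (columns A to C) and the matching completer targets (columns D to F).

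Hungary is one of the potential countries. France, Switzerland, Austria, Sweden and the Netherlands are confirmed, and at most nine countries will take part.

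**The concern.** Table 3 should follow from Tables 1 and 2 under the factors in section 9.2.3. In the Hungarian row it plans more prescriber invitations than there are panel members, in a country with no distribution list. In two pairs of countries, the one with fewer recipients and the smaller panel gets the larger allocation.

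What is at stake is mostly at country level. Implementation is to be described for each country (section 9.7.4), and knowledge and behaviour are to be analysed by country (section 9.7.6). A target that cannot be met, or a small allocation in a country with wide distribution, weakens those descriptions. It also leaves the stated safeguard against selection bias without support in these rows.

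**Working it through.** **The plan's own total.** Response rate: 0.17 × 0.26 = 4.4% and 0.17 × 0.40 = 6.8%. Invitations for 400 completers: 400/0.068 = 5,882 and 400/0.044 = 9,091, which agree with the printed 6,000-9,000. Columns B and C are 75-90% and 10-25% of column A (Hungary: 0.75 × 250 = 187.5, 0.90 × 400 = 360; 0.10 × 250 = 25, 0.25 × 400 = 100). The total is sound; the question is its division between countries.

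**Recipients from Table 1.**

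- Poland: 326 + 705 + 97 + 48 + 53 + 163 = 1,392. This mixes people and centres; haematologists and oncologists alone are 326 + 705 = 1,031.
- Sweden: 293 + 104 = 397.
- Austria: 29 + 16 + 9 + 1 + 2 + 9 = 66, without an uncounted regional donation centre and 58 pharmacies listed for information. With the pharmacies it is 124.

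**Side by side.**

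| Country | Recipients | Panel | Column A | Column B | B / panel |
|---|---|---|---|---|---|
| Hungary | none yet | 120 | 250-400 | 190-360 | 1.58-3.00 |
| Poland | 1,392 | 288 | 100-150 | 75-135 | 0.26-0.47 |
| Austria | 66 | 538 | 250-400 | 190-360 | 0.35-0.67 |
| Sweden | 397 | 594 | 100-150 | 75-135 | 0.13-0.23 |

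Hungary is the only one of the eleven countries whose planned invitations exceed its panel. The next highest is Finland, with 100/156 = 0.64 to 150/156 = 0.96 on column A.

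**Hungary's shortfall.** Prescriber invitations: 190 − 120 = 70 to 360 − 120 = 240 too many. Even with all 100 non-prescriber invitations, the maximum is 120 + 100 = 220, below the column A minimum of 250. Expected prescriber completers: 120 × 0.044 = 5.3 to 120 × 0.068 = 8.2, against a target of 8-14.

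**The two orderings.** Poland exceeds Hungary on panel (288 v 120) and volume, and its distribution is earlier (August-September 2020 v none). Sweden exceeds Austria on panel (594 v 538) and volume (397 v 66, or 124 with pharmacies); both first distributed in June 2020. The minimum and maximum for Hungary and Austria are 250/100 = 2.5 and 400/150 = 2.7 times those for Poland and Sweden.

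**Effect on the pooled result.** Assume that 10 of 400 completers move between countries whose correct-answer rates differ by 20 to 30 percentage points. The pooled proportion moves by 10/400 × 20 = 0.5 to 10/400 × 30 = 0.75 points.

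**The case against.** The best defence is that distribution volume is only one of the stated factors, that Table 3 is labelled as an estimate to be adjusted to response, and that Hungary may not be selected. This has force, and it rules out several stronger readings.

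- A reader might infer that the whole table contradicts the volume rule, with Switzerland ("About 50 maximum physicians in Onco/Haematology, blood banks (BB) and blood donation centres", yet 250-400 invitations) as the main example. The documents do not support this. Switzerland's panel is 1,135 against Poland's 288, and section 9.9 names the potential pool as the basis. Across the ten countries with recipient counts, invitations rise with volume (rank correlation 0.71).
- A reader might infer that countries with wide distribution are generally under-represented. Italy, the UK, Germany and France have the largest recipient counts. They hold 5,000 of 6,300 (79%) to 7,000 of 9,050 (77%) of the invitations, using the sums of the rows.
- A reader might infer that answers from people who never received the materials are useless. Non-receipt is itself an implementation result. Every respondent is asked about receipt, and section 9.7.6 plans a comparison of those who did and did not receive the materials, if numbers allow.
- A reader might infer that Hungary's invitations can never be sent. Table 2 is the current panel, and a distribution list could exist after launch. The protocol gives no number for it, so the shortfall holds for the sources now documented.

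The defence does not rescue the rows in question. Adjusting to response does not add panel members. Panel size, volume and date all fail to put Hungary above Poland, and panel size and volume fail to put Austria above Sweden. Country population is also a stated factor, but the protocol gives no population figures to check it by. Table 1 marks Sweden as not reimbursed, but section 9.9 says that allocation does not follow volume of use.

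**Conclusion.** The point holds for specific rows. On the documented inputs, Hungary's row cannot be met: it is 70-240 prescriber invitations over the panel, with about 5-8 expected prescriber completers against a target of 8-14. The Hungary-Poland and Austria-Sweden orderings run against both panel size and distribution volume. Section 9.9 describes launches in 2020 or by early 2021, while section 9.2 keeps Hungary, with launch planned for November 2021, as a candidate.

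The Hungarian shortfall rests on the current panel and matters only if Hungary is chosen. Austria and Sweden are both confirmed, so that mismatch does not depend on country selection. The recipient counts mix people, departments and centres, but both orderings survive the alternative counts shown. The effect on the pooled 80% criteria is under one percentage point on the assumption stated, so this is a correction to planning and country-level targets and does not threaten the main conclusion.

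**What to change.** 1. **Hungary.** Cap prescriber invitations at the available panel plus any distribution list that exists by then (at most 120 on current figures) and restate columns A to F, or remove the country. With B = 120 and the plan's own shares, A = 120/0.90 = 133 to 120/0.75 = 160 and C = 13 to 40. Then D = 133 × 0.044 = 6 to 160 × 0.068 = 11, E = 5 to 8, and F = 13 × 0.044 = 0.6 to 40 × 0.068 = 2.7, or about 1 to 3. This is close to the rows already given to Finland, Sweden and Poland.
2. **Poland and Sweden.** Reconcile these rows with the factors in section 9.2.3, using their unused panel for the freed invitations, or state the basis actually used. At the top of their present ranges, 288 − 135 = 153 and 594 − 135 = 459 panel members remain. Together that is 612, more than the 240 that Hungary could release.
3. **Section 9.9.** Align the launch statement with the final country list.

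Do not reallocate the whole table in proportion to Table 1, and do not cut Switzerland. Listed recipients total about 26,100, so strict proportionality would give Switzerland 50/26,100 = 0.2% of 6,000-9,000, or about 11-17 invitations and about one completer, in a confirmed country.

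The cost is a revision of one table and one sentence before fieldwork, with no extra invitations overall. The downside is fewer Hungarian respondents: about 6-11 in place of the planned 10-15, or none if the country is removed.
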